### Clinical research program:

The study was carried out on the basis of the KGP at the RVC "Multidisciplinary Hospital No. 3 of the city of Karaganda". Venue: intensive care unit.

To identify nutritional deficiency, there are screening methods recommended by the international clinical nutrition associations ASPEN (American Society for Parenteral and Enteral Nutrition - ASPEN) and ESPEN (European Society for Parenteral and Enteral Nutrition - ESPEN), including questioning patients, using standard anthropometric and laboratory data, which makes it possible to assess nutritional status and the degree of its impairment.

At the first stage, the clinical condition of the patient was assessed using the Nutritional Risk Screening (NRS, 2002), Subjective Global Assessment (SGA) and Nutritional Risk Index (NRI) protocols before surgery and on the 5th, 10th, 15th day after surgery .

A comparative assessment of the clinical effectiveness of the use of types of nutritional nutrition in a complex of therapeutic measures after these operations in the hepatopancreatoduodenal zone was carried out.

Some nutritional status indicators available for determination at the Oncology Clinic were assessed - body mass index (weight measurements were carried out before surgery, on the **5th, 10th and 15th** days), basal metabolic rate (calculated using the Harris-Benedict equation, based on anthropometric data of the patient (gender, age, weight and height).), laboratory parameters: blood hemoglobin, lymphocytes, total protein, serum albumin, serum transferrin, total bilirubin and direct, ALT, AST, which are related to the traditional method for assessing nutritional status.

Additionally, we assessed the duration of postoperative gastrostasis, the timing of the onset of intestinal motility, the appearance of stool, the return to a normal diet, the duration of patients' stay in the ICU, the repeated admission of patients to the ICU and the duration of the postoperative bed-day, and the incidence of complications was calculated.

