## **Methods of statistical data analysis**

All patients hospitalized for special treatment with a verified diagnosis of a malignant neoplasm were subjected to the study in the abdominal department of the KGP at the Regional Oncological Dispensary, Karaganda.

The quantitative and qualitative indicators obtained during the study were analyzed using descriptive and analytical statistics methods. For statistical processing of qualitative (diagnosis codes, dichotomous data) and quantitative variables: symptom intensity, severity, frequency of occurrence, we used the calculation of the median level (Me) with 25%-75% quartiles (Q25; Q75) and the calculation of the arithmetic mean (M) with error (m) and 95% confidence interval (95% CI), standard deviation (s). Quantitative variables were checked for normality of distribution using the Kolmogorov-Smirnov test, as well as the module of Skewness and Kurtosis for quantitative variables  $| \leq 2 |$ . Differences in the 3 groups of patients for quantitative variables corresponding to a normal distribution were identified using the Student's t test for unrelated groups, first for 3 or more groups, and then in pairs for each pair using the Student's t test. Differences for rank variables, or quantitative but not normally distributed for unrelated groups, were determined by the Kruskal-Wallis test or median test for 3 groups, and then pairwise or non-parametric Mann-Whitney test for each of the 3 pairs (groups 1 and 2, groups 1 and 3, groups 2 and 3), and for related groups (dynamic observations) by the Kendall test for 3 groups and then by the Wilcoxon test (Wilcoxon) for each of the 3 pairs (baseline, after 5 days and after 10 days).

Correlation was performed for quantitative variables according to Pearson and for rank variables according to Spearman. Statistical processing of the results was carried out using the Statistica program version 10.

**Results and discussion.** The nutritional status of patients in all three groups before surgery and during the 10-12 days of the postoperative period according to the methods of assessing nutritional status NRS, SGA and NRI was assessed as normal, moderate and severe malnutrition

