As can be seen from the presented data, in the preoperative period, according to the SGA assessment, 24 patients in the enteral group, 19 patients in the parenteral group, and 17 patients in the mixed group had normal nutritional status before surgery, with variations relative to patients with moderate to severe malnutrition. Assessment of nutritional status before surgery using the NRI scale allowed us to confirm the nutritional status of the vast majority of patients in all groups as relatively normal

Thus, in 62 of the 91 patients examined, the NRI was assessed as true negative (normal nutritional status), in 26 as true positive (moderate malnutrition), and in 3 as severe malnutrition. Data from the NRI method during this time period had a strong correlation with the results of the SGA scale ( $p < 0.005$ ).

On the 10-12th day of the postoperative period in patients of the “enteral” group, the results of the assessment on the SGA scale remained unchanged; according to the NRI rating scale, there was an increase in “moderate malnutrition” per patient (25%).

With parenteral nutritional support, 17 patients had “normal nutrition”, 14 patients had moderate malnutrition, with regression of “severe malnutrition” in 1 patient. In the mixed nutrition group, there was a complete elimination of signs of “severe malnutrition” by 100% according to the given scales ( $p < 0.005$ ).

In patients of all study groups, throughout the entire period of nutritional support, fluctuations in the level of basal metabolism were observed in average values of  $335.89 \pm 53.6$  kcal/day (13.44%) from the initial value - 1-2 days of the postoperative period and were due to variability body mass index and the dynamics of the temperature curve after surgery.

In patients in the groups with enteral and parenteral nutrition, by the end of these types of energy subsidies (days 10-15), the level of basal metabolism was observed to approach its initial values -  $2500.1 \pm 353.4$  kcal/day and  $2350.0 \pm 330.5$  kcal/day days accordingly. With a mixed type of nutrition, there was a statistically significant decrease in the level of basal metabolism by 6.78% ( $2250.0 \pm 105.2$  kcal/s), which allows us to conclude that patients' energy costs are more effectively covered with this option of nutritional support in a comparative aspect with isolated types nutrition ( $p < 0.03$ ).

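### The p<0.005 for elimination of severe malnutrition in the mixed group has no stated scale, comparison or test and cannot validly be the NRI-severe change from before surgery; Conclusion 1 ranks the groups on NRI and SGA with no between-group result reported

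*Combined protocol and SAP*

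**What the plan says.** The report grades nutritional status as normal, moderate or severe on NRS, SGA and NRI. Under Clinical research program, the assessments are scheduled by "protocols before surgery and on the 5th, 10th, 15th day after surgery", which makes four visits.

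Results and discussion (within the section Methods of statistical data analysis) gives these figures:

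- NRI before surgery, all groups together: 62 normal, 26 moderate, "and in 3 as severe malnutrition". There is no split by group.
- SGA normal before surgery: 24 enteral, 19 parenteral, and "17 patients in the mixed group had normal nutritional status before surgery". The moderate/severe split is not given.
- Parenteral, days 10-12: 17 normal, then "14 patients had moderate malnutrition, with regression of" the severe grade in 1 patient. The scale is not named.
- Mixed, days 10-12: "In the mixed nutrition group, there was a complete elimination of signs of" severe malnutrition "by 100% according to the given scales", followed by p<0.005.

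The methods text names tests by type of variable, not by result. For repeated measures, differences were assessed "by the Kendall test for 3 groups and then by the Wilcoxon test (Wilcoxon) for each of the 3 pairs", the pairs being formed from baseline, day 5 and day 10. For independent groups: "Differences for rank variables, or quantitative but not normally distributed for unrelated groups, were determined by the Kruskal-Wallis test" or the median test, then Mann-Whitney for each pair.

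Conclusion 1 says that, on NRI and SGA, mixed support was more effective than isolated enteral and isolated parenteral support. It cites no p-value or test.

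**The concern.** Two things look wrong. First, a p-value below 0.005 is attached to the disappearance of a category that, on the one scale whose severe count is printed, held 3 patients in the whole study. So small a number of changes cannot ordinarily yield so small a p-value.

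Second, Conclusion 1 is a three-group efficacy ranking, and research objective 1 is exactly this comparison. What the text reports on NRI and SGA after surgery is a change described separately in each group, plus one p-value of unstated origin in the mixed-group sentence. A change inside one group cannot rank three groups. If the p-value is within-group, nothing reported supports the ranking. If it is between-group, the text does not say so, and it cannot be a valid comparison of falls in NRI-severe from before surgery. Either way a reader cannot tell whether any analysis stands behind the first conclusion.

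**Working it through.** **Inputs.** Group sizes 31 / 30 / 30 (Research objectives). NRI before surgery 62 + 26 + 3 = 91, so the categories account for everyone. The number NRI-severe before surgery in the mixed group, k, is therefore at most 3. If the parenteral patient who left the severe category was graded on NRI, k is at most 2.

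**Most favourable case.** All 3 are in the mixed group (n=30), all leave the severe category by the first postoperative visit, and nobody enters it. All p-values are two-sided or omnibus.

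**Target figure.** p<0.005. It is not reproduced by any of the following.

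Within-group tests that the report names:

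- Kendall's test (equivalent to Friedman), severe yes/no over m visits. With k patients severe only at the first visit, the tie-corrected statistic is Q = k(m-1) on m-1 degrees of freedom. Four visits: Q = 3×3 = 9, df 3, p = 0.029. Three visits: Q = 3×2 = 6, df 2, p = 0.050.
- Wilcoxon with ties. All k changes are equal and in one direction, so z² = k. For k=3, p = 0.083.
- With k=2: Kendall 0.11 (four visits) or 0.14 (three visits), Wilcoxon 0.16.

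Within-group tests that it does not name:

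- Exact paired test: 2×0.5³ = 0.25.
- 3/30 against 0/30 treated as unpaired: Fisher 0.24, chi-square 0.076, likelihood-ratio 0.038, angular-transformation z 0.013.

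Between-group tests that the report names, applied to leaving the severe category, with 3 changes in mixed and none elsewhere:

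- Expected changes: 3×31/91 = 1.022 enteral, 3×30/91 = 0.989 in each other group.
- Pearson chi-square = (91/88) × (1.022 + 0.989 + (3-0.989)²/0.989) = 6.31, df 2, p = 0.043. This is also the median test here.
- Kruskal-Wallis H = (90/91) × 6.31 = 6.24, df 2, p = 0.044.
- Mann-Whitney, mixed against enteral: 0.073.
- If mixed had 2 changes and parenteral 1, Kruskal-Wallis gives 0.35.

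The smallest p-value from a named test is 0.029, and 0.029/0.005 is about 6.

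**Could SGA give it?** In the mixed group 30-17 = 13 patients were not SGA-normal. The number of one-way changes needed for p<0.005 is:

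- Kendall, four visits: 5 (4 give 0.0074, 5 give 0.0018).
- Kendall, three visits: 6 (5 give 0.0067, 6 give 0.0025).
- Wilcoxon: 8 (7 give 0.0082, 8 give 0.0047).
- Exact paired: 9 (8 give 0.0078, 9 give 0.0039).

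So 5 to 9 of the 13 (38% to 69%) would have to have been SGA-severe. That is possible, but the count is not stated.

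**Parenteral counts.** 17 + 14 = 31 against n=30, if both numbers are from one scale.

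**The case against.** A reader might infer that the printed p-value is simply impossible. The documents do not support that. The ceiling of 3 applies only to NRI-severe before surgery. Day 5 against day 10 is one of the pairs listed in the methods, and the day-5 NRI-severe count is not given. SGA, NRS, or a shift over all three categories could also be the source.

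A reader might also take the p-value to be within-group because of where it stands. The sentence does not say, which is why both readings are computed above.

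Nor is it true that no calculation starting from 3 patients goes below 0.005. A likelihood-ratio test on 3/3 against 0/3 gives 0.0039, and the words about 100% elimination might suggest that denominator. But those patients were selected for being severe, so the baseline of 100% is fixed by construction, and every expected count is 1.5. An angular test of mixed against enteral and parenteral pooled also gives 0.0039, but the documents name neither the test nor the pooling. Counting three later visits of the same 30 patients as 90 independent patients gives 0.0024 by chi-square. None of these is a sound basis for the claim.

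The results text refers to presented data that do not appear in the extracted document, and a figure is missing. Group counts, and the scale behind the parenteral 17 and 14, may be there. So the total of 31 is something to check, not a demonstrated extra patient. No exhibit can raise the preoperative NRI ceiling above 3.

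Finally, the mixed group had the fewest SGA-normal patients before surgery (17/30, against 24/31 and 19/30). It would go too far to call this a demonstrated imbalance: the three-group chi-square is 3.06, df 2, p = 0.22. It matters for the choice of analysis, not as evidence against the claim.

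**Conclusion.** The point holds in a bounded form and must be fixed. The p<0.005 is unattributed, and it cannot validly be the fall in NRI-severe from before surgery to days 10-12: in the best case the report's own tests give 0.029 to 0.083 within the group and 0.043 to 0.044 across the three groups. This rests on the printed NRI counts being preoperative and complete (they add to 91), on n=30 in the mixed group, and on placing all 3 severe patients there. Placing fewer there makes the p-values larger.

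Separately, Conclusion 1 ranks three groups on NRI and SGA, and the available text reports no between-group result on either scale, although suitable rank tests are named in the methods. The documents do not show that mixed support was no better. They show that the ranking has no identified support.

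**What to change.** 1. From existing records, tabulate normal, moderate and severe counts by scale, group and day, adding to 31 / 30 / 30. State the scale behind the parenteral 17 and 14.
2. Attribute p<0.005 to its scale, its comparison (within or between groups, and between which days) and its test, or replace it with the p-value from the true counts.
3. Compare the groups at days 10-12 on NRI and on SGA with the tests already named (Kruskal-Wallis, then Mann-Whitney), taking baseline category into account, for example by stratifying on it or by ordinal regression with baseline as a covariate. Do not use unadjusted change scores: a patient who starts normal cannot improve, and 13/30 mixed patients were not SGA-normal at baseline against 7/31 enteral, so raw change favours the group with more room to improve.
4. Keep the superiority wording in Conclusion 1 only if that comparison supports it. Otherwise report the changes in each group without ranking them.

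The cost is a recount, a small reanalysis of data already held, and reworded text. The downside is that the headline claim may weaken.

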### Research objectives:

1. To conduct a comparative assessment of the dynamics of nutritional deficiency and nutritional status of patients operated on for malignant tumors of the hepatopancreatoduodenal zone in the early postoperative period during isolated enteral, isolated parenteral and mixed types of nutritional support.
2. To analyze the dynamics of the state of protein and carbohydrate metabolism, the consistency of liver function in cancer patients operated on for malignant tumors of the hepatopancreatoduodenal zone, against the background of isolated enteral, isolated parenteral and mixed type of nutritional support in the early postoperative period.
3. To determine the degree of effectiveness of these methods of nutritional support in this category of patients based on the totality of the results of assessing nutritional status and the dynamics of the level of basal metabolism in these patients in the early postoperative period.

Researched 91 patients, will be divided into 3 groups:

1. The first group (n=31) included patients who received enteral nutrition (EN) after surgery.
2. The second group (n=30) included patients receiving parenteral nutrition (PN).
3. The third group (n=30) receiving mixed nutrition (MN), as is commonly considered the method of partial parenteral nutrition, in the early postoperative period.

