### **Conclusion:**

1. According to the NRI nutritional status assessment scales, the SGA mixed type of nutritional support at the time of transfer of patients to the specialized department and upon completion of this area of intensive therapy in the specialized department by 12-15 days of the postoperative period showed higher effectiveness in stabilizing the condition and maintaining the patients' caloric intake in a comparative aspect with the group of isolated enteral nutrition and parenteral nutrition.
2. Throughout the entire period of isolated enteral, parenteral and mixed nutritional support, all patients (100%) showed a relatively constant level of total blood protein.
3. In patients of all three groups, throughout the entire period of nutritional support, fluctuations in the level of basal metabolism were observed, which was due to the variability of body mass index and the dynamics of the temperature curve after surgery. In patients in the groups with enteral and parenteral nutrition, by the end of nutritional support (days 15-20), the level of basal metabolism was observed to approach its initial values. With a mixed type of nutrition, a statistically significant decrease in the level of basal metabolic rate was observed, which suggests a more effective coverage of the energy costs of patients with this option of replenishing nutritional ingredients.

**Researcher:** [name], PhD student KSMU

[contact].

e-mail: [contact].

[figure not shown]
Signature  17.03.2020

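### Conclusion 1 ranks mixed feeding above enteral and parenteral feeding on NRI/SGA, but the readable results never compare the three arms on one scale and one set of categories

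*Combined protocol and SAP*

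**What the plan says.** The report's Results and discussion, printed under Methods of statistical data analysis, says that NRS, SGA and NRI sorted patients into normal, moderate and severe malnutrition. The arm sizes are 31 enteral, 30 parenteral and 30 mixed (report, Research objectives: "The first group (n=31) included patients who received enteral nutrition (EN) after surgery", "The second group (n=30) included patients receiving parenteral nutrition (PN", "The third group (n=30) receiving mixed nutrition (MN").

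Before surgery, SGA is given by arm: "24 patients in the enteral group, 19 patients in the parenteral group, and 17 patients in the mixed group had normal nutritional status". NRI is given only for the three arms pooled: 62 normal, 26 moderate, 3 severe.

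At days 10-12 the arms are described as follows.
- **Enteral:** "the results of the assessment on the SGA scale remained unchanged; according to the NRI rating scale, there was an increase in" moderate malnutrition, apparently by one patient, printed with 25%.
- **Parenteral:** "With parenteral nutritional support, 17 patients had" normal nutrition, 14 had moderate malnutrition, and severe malnutrition regressed in 1. No scale is named.
- **Mixed:** "In the mixed nutrition group, there was a complete elimination of signs of" severe malnutrition, given as 100% on the scales in question with p<0.005. The readable text has no normal or moderate count, and no test or contrast is named.

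Conclusion item 1, which refers to days 12-15, says that mixed support "showed higher effectiveness in stabilizing the condition and maintaining the" caloric intake, relative to both isolated types. The methods section does name a between-arm procedure for rank variables (Kruskal-Wallis or median test, then pairwise Mann-Whitney). The readable text identifies no such between-arm result for SGA or NRI after support, and it gives no NRS figures.

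**The concern.** A ranking of three arms needs the same outcome, on the same scale, in each arm. Here the arm ranked first is described after support only by the emptying of its worst category. A patient who moves from severe to moderate is still malnourished, so an empty severe category says nothing about how many patients were well nourished. The two percentages and the p-value make the result look large, yet the text does not show how many patients lie behind them.

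This is the report's first conclusion and it answers research objective 1, the comparison of nutritional status over time between the three types of support. If it cannot be supported, the main comparative claim on nutritional status goes with it.

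**Working it through.** **Inputs.** Arm sizes 31, 30, 30 (report, Research objectives). All other counts come from Results and discussion.

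**1. Do the printed counts add up?**
- NRI before surgery: 62 + 26 + 3 = 91. This agrees with the total.
- Parenteral, days 10-12: 17 + 14 = 31 against n = 30. One count or the denominator is wrong. The normal share is 17/30 = 56.7% or 17/31 = 54.8%, depending on which.

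**2. The enteral 25%.** If one extra patient is a 25% increase, the base is 1/0.25 = 4, that is 4 moderate cases rising to 5. It cannot be a share of the arm, since 0.25 × 31 = 7.75 is not a whole number. Over the arm, one patient is 1/31 = 3.2% (exact 95% CI 0.1 to 16.7%).

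**3. The mixed 100% and p<0.005, on NRI.** NRI had 3 severe cases in all arms together, and their split by arm is not printed. The case most favourable to the report puts all 3 in the mixed arm, at most 3/30 = 10% of it.
- Within the arm, 3 to 0: exact McNemar p = 2 × 0.5³ = 0.25 two-sided, 0.125 one-sided, 0.083 by the asymptotic form.
- Between two arms, 3/30 against 0/30: Fisher p = 0.24.
- Number needed for exact two-sided p<0.005: 2 × 0.5⁸ = 0.0078 and 2 × 0.5⁹ = 0.0039, so 9 patients. One-sided or asymptotic, 8.

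The printed p<0.005 is therefore not reproduced by loss of the severe category on NRI. On SGA it cannot be checked, because severe counts on SGA are not printed. The only bound is that 30 − 17 = 13 mixed patients were not normal on SGA before surgery.

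**4. Baseline.** SGA-normal before surgery:

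| Arm | Normal | Share |
|---|---|---|
| Enteral | 24/31 | 77.4% |
| Parenteral | 19/30 | 63.3% |
| Mixed | 17/30 | 56.7% |

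The three-arm chi-square p is 0.22, and enteral against mixed gives Fisher p = 0.11. In arms of this size, a non-significant difference of about 21 percentage points is still large enough to distort a comparison of levels.

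**5. What a level comparison could show.** Take enteral SGA as 24/31 after support, inferred from the statement that it did not change. The mixed count is unknown, so it is varied:

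| Mixed normal after support | Share | Higher level | Net change, mixed (enteral 0) |
|---|---|---|---|
| 17/30 | 56.7% | enteral | 0 |
| 20/30 | 66.7% | enteral | +3 |
| 23/30 | 76.7% | enteral | +6 |
| 24/30 | 80.0% | mixed | +7 |

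For counts from 18 to 23, enteral leads on level while mixed leads on change. Without the mixed count and without baseline adjustment, the order of the arms is undetermined.

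**The case against.** **A table may be missing.** The text breaks off after listing the categories and then refers the reader to presented data. Figures are dropped elsewhere in the report. The mixed counts, and NRS results, may have been there. This stands, so only absence from the readable text can be claimed. It does not remove the total of 31, the unnamed parenteral scale, the two percentages or the unexplained p-value, all of which are in the prose.

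**The p-value may refer to something else.** It is attached to more than one scale, and it could come from a within-arm test over all three categories, including moves from moderate to normal. That is possible. It would then be a change within one arm, which does not establish superiority over two others.

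**The arms do overlap in what is reported.** The parenteral arm is described on all three categories, severe is mentioned for both parenteral and mixed, and an unchanged SGA in the enteral arm covers every category. A reader might infer that each arm was judged on its own private category. That goes too far. The exact statement is that no single scale and set of categories is shown for all three arms.

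**A reader might also infer that enteral feeding came out ahead on share normally nourished.** The documents do not support this. Against mixed feeding there is no count to compare. Against parenteral feeding, 24/31 and 17/30 give Fisher p = 0.11, with the parenteral scale unnamed and its counts inconsistent. The enteral lead was present before surgery, and enteral SGA did not change.

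**Conclusion.** The concern holds for the printed text. Conclusion 1's ranking on NRI and SGA cannot be verified, because the mixed arm is characterised only by loss of the severe category and no between-arm test after support is identified. On NRI that category held at most 3 of the 30 mixed patients, and its loss gives p = 0.25 at best by the exact two-sided test, against the printed p<0.005. The enteral 25% is one patient, 3.2% of the arm. The parenteral counts exceed the arm by one.

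This does not show that mixed feeding was no better, or that enteral feeding was better. The data may yet support the conclusion.

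The verdict rests on three readings: the enteral NRI change is one patient; unchanged SGA means 24 of 31 still normal; and the pooled NRI total of 3 severe is correct. The first two affect only the illustrations. The third carries the result on NRI. The SGA part of the p-value remains open.

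**What to change.** 1. Add one table of normal, moderate and severe counts by arm, by scale (NRS, SGA, NRI) and by visit (before surgery, days 5, 10 and 15), with the arm size as denominator and any missing assessments shown.
2. Reconcile the parenteral total of 31 with n = 30, and name the scale.
3. Name the test, the scale and the contrast behind p<0.005.
4. Compare the arms at day 10 on one ordinal outcome with baseline category as covariate, reporting odds ratios with 95% confidence intervals. Merge severe with moderate if severe is too sparse. At minimum, apply the Kruskal-Wallis and Mann-Whitney tests already named in the methods to change from baseline.
5. Replace the 25% and the 100% with counts over arm size.
6. Align the visit cited in Conclusion 1 (days 12-15) with the visit analysed. Withdraw or qualify the ranking so that it says what the comparison shows.

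The cost is one table and one model on assessments that the clinical research program says were made. The superiority wording may not survive.

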### **3. Age.**

Age from 20 to 75 years.

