Some nutritional status indicators available for determination at the Oncology Clinic were assessed - body mass index (weight measurements were carried out before surgery, on the 5th, 10th and 15th days), basal metabolic rate (calculated using the Harris-Benedict equation, based on anthropometric data of the patient (gender, age, weight and height).), laboratory parameters: blood hemoglobin, lymphocytes, total protein, serum albumin, serum transferrin, total bilirubin and direct, ALT, AST, which are related to the traditional method for assessing nutritional status.

Additionally, we assessed the duration of postoperative gastostasis, the timing of the onset of intestinal motility, the appearance of stool, the return to a normal diet, the length of patients' stay in the ICU, the readmission of patients to the ICU and the duration of the postoperative bed-day, and the incidence of complications was calculated.

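### The reported basal metabolism values do not fit the stated Harris-Benedict definition: they are said to follow temperature, and their level and changes are implausible for it, so the 6.78% inference for mixed nutrition is unsupported

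*Combined protocol and SAP*

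**What the plan says.** The protocol (section III, Methods and procedures) lists "basal metabolic rate (calculated using the Harris-Benedict equation, based on anthropometric data of the patient (gender, age, weight and height" among the indicators, and the Report (Clinical research program) repeats the definition: "calculated using the Harris-Benedict equation, based on anthropometric data of the patient (gender, age, weight and height". Weight, which also enters this calculation, has a fixed schedule: "weight measurements were carried out before surgery, on the 5th, 10th and 15th days".

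The Report's Results, printed under Methods of statistical data analysis, give a mean fluctuation in all groups of 335.89 ± 53.6 "kcal/day (13.44%) from the initial value - 1-2 days of the postoperative period", and say that these fluctuations "were due to variability body mass index and the dynamics of the temperature curve after surgery". Values at the end of support are 2500.1 ± 353.4 (enteral), 2350.0 ± 330.5 (parenteral) and 2250.0 ± 105.2 (mixed; the unit is printed as kcal/s and read here as kcal/day). For the mixed group "there was a statistically significant decrease in the level of basal metabolism by 6.78" per cent (p < 0.03), and from this the Report infers that mixed support meets energy needs better than either isolated type.

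Conclusion, item 3, repeats both the inference and the cause, "which was due to the variability of body mass index and the dynamics of the temperature curve after surgery". Objective 3 judges effectiveness on two components together: nutritional status and the course of basal metabolism.

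**The concern.** The definition and the results disagree about what determines the variable. A quantity computed from sex, age, weight and height has no route by which temperature can enter, and nothing in the protocol or Report describes a temperature, stress or activity factor, or a measured energy expenditure. The values also look far too high for basal metabolism in a surgical cancer population of both sexes.

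The meaning of the mixed-group result is at stake. If some factor was included, the fall may only track that factor, for example resolving fever. If the plain equation was used, a fall in the same patients can only mean weight loss. Neither reading shows better coverage of energy needs.

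**Working it through.** **Inputs from the documents.** 335.89 kcal/day and 13.44%; end values 2500.1, 2350.0 and 2250.0; fall of 6.78%; group sizes 31, 30 and 30; both sexes; "Age from 20 to 75 years"; NRI before surgery normal in 62, moderate malnutrition in 26 and severe in 3.

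**Assumed.** The documents print no coefficients, weights or heights. Two common versions of the equation were used. Their weight slopes are about 13.75 (men) and 9.56 (women) kcal/day per kg in the original, and 13.40 and 9.25 in the revised version.

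**1. The Report's percentage.** 335.89 / 2500.1 = 13.435%, which rounds to 13.44%; equivalently 335.89 / 0.1344 = 2499.2. It does not reproduce on 2350.0 (14.29%), 2250.0 (14.93%) or the weighted mean (31 × 2500.1 + 30 × 2350.0 + 30 × 2250.0) / 91 = 2368.2 (14.18%). The percentage is sound on a base of about 2500 kcal/day.

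**2. The mixed-group fall.** Taking 6.78% as relative to that group's own starting value, which is not printed: 2250.0 / (1 − 0.0678) = 2413.6, a fall of 2413.6 − 2250.0 = 163.6 kcal/day.

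**3. Weight change needed.** Sex and height are fixed, and age is effectively fixed over the support period. So change in weight = change in kcal/day ÷ slope.

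| Change | Men | Women |
|---|---|---|
| 335.89 kcal/day | 335.89/13.75 = 24.4 kg; 335.89/13.40 = 25.1 kg | 335.89/9.56 = 35.1 kg; 335.89/9.25 = 36.3 kg |
| 163.6 kcal/day | 163.6/13.75 = 11.9 kg; 163.6/13.40 = 12.2 kg | 163.6/9.56 = 17.1 kg; 163.6/9.25 = 17.7 kg |

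**4. Weight needed for the level.** Weight = reference weight + (target − equation value at the reference weight) ÷ slope.
- Man, 60 years, 175 cm (75 kg gives 1568 original, 1592 revised). For 2250: 75 + 682/13.75 = 124.6 kg, or 75 + 658/13.40 = 124.1 kg. For 2500.1: 75 + 932.1/13.75 = 142.8 kg, and the same for the revised version.
- Woman, 60 years, 165 cm (75 kg gives 1397 original, 1392 revised). For 2250: 75 + 853/9.56 = 164.2 kg, or 75 + 858/9.25 = 167.8 kg. For 2500.1: 75 + 1103.1/9.56 = 190.4 kg, or 75 + 1108.1/9.25 = 194.8 kg.
- Other heights at age 60: 119-146 kg for men of 165-190 cm and 161-198 kg for women of 155-180 cm.
- Lowest weight found over ages 20-75, for the lowest reported mean: a man of 20 years and 190 cm (90 kg gives 2120), 90 + 130/13.75 = 99.45, about 99 kg.

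**5. Comparison with a group mean.** Assume age 60, half of each sex, men 175 cm and women 162 cm. At BMI 25 the equation gives 1446-1455 kcal/day, so the printed means are 2250/1455 = 1.55 to 2500.1/1446 = 1.73 times that. At BMI 40 it gives 1945-1950, and the ratio is still 2250/1950 = 1.15 to 2500.1/1945 = 1.29.

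**6. Timing.** Whether days 1-2 are read as the reference time or as the time of the fluctuation, a value by the stated equation needs a weight then. The schedule has none between the preoperative measurement and day 5.

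**The case against.** Body mass index is named before temperature as a cause, and it is compatible with the equation because weight is an input. The mention of temperature may be loose narrative in a rough translation; the Report offers similar causal asides about protein and bilirubin. No weights or heights are given, so the argument on magnitude rests on assumed coefficients and assumed bodies, and a large young man could reach 2250 kcal/day.

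Most of this is fair, but it does not remove the problem. Weight alone would have to change by 24-36 kg to give the reported swing. The temperature attribution appears in the Results and again in the Conclusion. The printed figures are group means in a mixed-sex population, so one feasible individual does not rescue them.

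The objection does rule out several stronger readings that a reader might infer:
- That a temperature or stress multiplier was applied and the figures are total energy expenditure. This would fit, but no text records it, and a calculation error or another equation is not excluded.
- That the levels are impossible under the equation. Without weights and heights, they are only implausible at group level.
- That the 13.44% is an arithmetic slip. It reproduces.
- That Objective 3 stands or falls on this variable. It also rests on nutritional status, and Conclusion 1 draws on NRI and SGA.

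**Conclusion.** The definition and the reported results conflict, and nothing in the documents reconciles them. On temperature and on the days 1-2 timing, this follows from the text alone. On size, it rests on the assumed coefficients, holds for both versions tested over ages 20-75 and the heights shown, and points the same way for level, swing and mixed-group fall. It is therefore very unlikely that the printed values are the declared outcome, but what they are remains unknown. The step from the 6.78% fall to better energy coverage, in the Results and in Conclusion 3, is unsupported. This needs correcting because it affects one of the two components of Objective 3 and the whole of the comparative claim in Conclusion 3.

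**What to change.** - Recompute basal metabolic rate for each patient by the stated equation, naming the version, before surgery and on days 5, 10 and 15. Use the preoperative value as baseline, because the days 1-2 value cannot be rebuilt from the scheduled weights.
- Report it by group and visit with mean weight change and the number of patients with data, so that a shift in who was measured is not read as a change.
- If the printed figures came from another formula or included factors, state these and rename the variable.
- Withdraw the 6.78% effectiveness inference from the Results and Conclusion 3 unless the recomputed values and the weight changes support it.

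The cost is a small reanalysis with no new patients. It is limited to patients whose weights were actually recorded, and the documents do not confirm that these are complete. The significant basal metabolism result may not survive.
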